APPENDIX 5. ADDITIONAL ADVERSE EVENT INVESTIGATIONS

1) Adverse Events at the Injection Site

- Injection site reaction (HLT)

2) Hepatic events

- Drug related hepatic disorders - comprehensive search (SMQ, broad and narrow)

3) Renal events

- Acute kidney injury (SMQ, broad and narrow)

4) New onset/worsening of diabetes

- Hyperglycemia/new onset diabetes mellitus (SMQ, narrow)
- Diabetic Complications (HLGT)
- Diabetes Mellitus (HLT)
- Carbohydrate tolerance analyses HLT, excluding PT “Blood glucose decreased”

5) Hypersensitivity

- Hypersensitivity' (SMQ, broad and narrow) excluding
 - PTs ‘infusion site %’ (‘infusion site dermatitis’, ‘infusion site eczema’, ‘infusion site hypersensitivity’, ‘infusion site rash’, ‘infusion site urticaria’, ‘infusion site vasculitis’) and
 - PTs ‘injection site %’ (‘injection site dermatitis’, ‘injection site eczema’, ‘injection site hypersensitivity’, ‘injection site rash’, ‘injection site urticaria’ and ‘injection site vasculitis’)

6) Neurological events and neurocognitive disorders

Neurological events

- Demyelination, (SMQ, broad and narrow)
- Peripheral neuropathy, (SMQ, broad and narrow)

Neurocognitive disorders

- Deliria (including confusion), (HLGT)
- Cognitive and attention disorders and disturbances, (HLGT)
- Dementia and amnesic conditions, (HLGT)

- Disturbances in thinking and perception (HLGT)
- Mental impairment disorders (HLGT)

7) Ophthalmologic events

- Optic nerve disorders, (SMQ, broad and narrow)
- Retinal disorders, (SMQ, narrow)
- Corneal disorders, (SMQ, narrow)

8) Major cardiovascular events (MACE)

Cardiac death

- Fatal SAEs in Cardiac disorders SOC
- Fatal SAEs in General disorder SOC: PTs 'Death', 'Sudden cardiac death', 'Cardiac death', 'Apparent death'

Cardiac arrest

- PT 'Cardiac arrest'

Non-fatal MI

- Myocardial infarction (SMQ, broad and narrow), nonfatal events only

Stroke

- Central Nervous System hemorrhages and cerebrovascular accidents (HLT), fatal and non-fatal events

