# 3.5. Exploratory Endpoints

The exploratory endpoints of this study are:

• Incidence of CV death, resuscitated cardiac arrest, non-fatal MI, and non-fatal stroke (ischemic and hemorrhagic)

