2.2. Objectives of Trial

Primary Objectives:

The primary objectives of this study are to evaluate the effect of inclisiran treatment on:

- LDL-C levels at Day 510
- Time adjusted percent change in LDL-C levels from baseline after Day 90 and up to Day 540 levels

Secondary Objectives:

The secondary objectives of this study are to evaluate the effect of inclisiran on:

- PCSK9, total cholesterol, ApoB and non-HDL-C at Day 510
- LDL-C and PCSK9 levels over time to Day 540
- Mean maximum reduction in LDL-C levels
- LDL-C and PCSK9 levels over time in individual subjects
- Other lipids, lipoproteins, apolipoproteins
- Proportion of subjects achieving prespecified LDL-C targets
- Safety and tolerability profile of inclisiran

Exploratory Objectives:

[figure not shown]
The exploratory objectives of this study are to collect/evaluate the effect of inclisiran on the following:

- Cardiovascular (CV) events such as CV death, resuscitated cardiac arrest, non-fatal myocardial infarction (MI), and non-fatal stroke (ischemic and hemorrhagic)

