6.4.6.3. Exploratory Endpoints

The exploratory endpoints of this study are:

- Incidence of CV death, resuscitated cardiac arrest, non-fatal MI, and stroke (ischemic and hemorrhagic)

A major cardiovascular event (MACE) is defined as the composite of CV death, resuscitated cardiac arrest, non-fatal MI, and stroke (ischemic or hemorrhagic). Refer to [Appendix 5](#) for details on the search terms used. The number and percentage of subjects with MACE or any of the individual events will be presented by treatment group.

- Proportion of subjects in each group with any LDL-C reduction from baseline at any visit (responders).

The number and percentage of subjects with any LDL-C reduction at any visit will be presented by treatment group. The odds ratio and 95% confidence interval for the odds ratio will be provided using a logistic regression model. The number and percentage of subjects with any LDL-C reduction will also be summarized at each visit.

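### The Appendix 5 search terms for MACE do not match the death and arrest components defined in SAP 6.4.6.3, and the change from non-fatal stroke to all strokes is not declared

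*SAP*

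**What the plan says.** **Definition.** SAP 6.4.6.3 states: "A major cardiovascular event (MACE) is defined as the composite of CV death, resuscitated cardiac arrest, non-fatal MI, and stroke (ischemic or hemorrhagic"). It refers to Appendix 5 "for details on the search terms used" and fixes the output: "The number and percentage of subjects with MACE or any of the individual events will be presented by treatment group".

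**Search terms.** SAP Appendix 5, item 8, has four blocks:
- Cardiac death: "Fatal SAEs in Cardiac disorders SOC", plus fatal SAEs in the General disorder SOC under the preferred terms 'Death', 'Sudden cardiac death', 'Cardiac death' and 'Apparent death'.
- Cardiac arrest: the single preferred term 'Cardiac arrest', with no condition on outcome.
- MI: the broad and narrow SMQ, restricted to non-fatal events.
- Stroke: "Central Nervous System hemorrhages and cerebrovascular accidents (HLT), fatal and non-fatal events".

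**Protocol.** Protocol 3.5 lists the exploratory endpoint as "Incidence of CV death, resuscitated cardiac arrest, non-fatal MI, and non-fatal stroke (ischemic and hemorrhagic"). The synopsis and Protocol 7.1.7 also limit stroke to non-fatal. The protocol lists these events but does not define a composite.

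**Elsewhere in the SAP.** The objectives in SAP 2.2 still read "Cardiovascular (CV) events such as CV death, resuscitated cardiac arrest, non-fatal myocardial infarction (MI), and non-fatal stroke (ischemic and hemorrhagic"), and SAP 3.8.7 uses the same non-fatal limit. SAP Section 8, which lists changes from the protocol, names one exploratory change, the added LDL-C responder endpoint. It does not mention stroke.

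**The concern.** CV events are collected as AE data (Protocol 7.1.7, SAP 3.8.7), and neither document describes adjudication. The Appendix 5 terms therefore are the endpoint in practice. SAP 6.4.6.3 also promises a count for each component, so every row is a planned result that will be read under its label.

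A program that follows Appendix 5 would print a row headed as CV death that leaves out some CV deaths and takes in deaths of unstated cause. It would also print a row headed as resuscitated arrest that contains arrests nobody survived. Fatal counts may well be small in a trial of this size, so a few misplaced cases could change how a row reads.

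**Working it through.** There is no stated MACE rate, count or power to reproduce. The check takes eight event types and asks whether each is counted under the protocol's list (any listed event), under the SAP 6.4.6.3 definition, and under the Appendix 5 terms.

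Coding assumptions, since the dictionary is not in the documents: fatal MI and fatal arrest code to the Cardiac disorders SOC; fatal stroke codes to the stroke HLT; other fatal vascular events code outside both.

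| Event in a subject with no other event | Protocol list | SAP 6.4.6.3 | Appendix 5 | Row(s) under Appendix 5 |
|---|---|---|---|---|
| Fatal MI | 1 | 1 | 1 | death |
| Fatal arrest, not resuscitated | 1 | 1 | 1 | death **and** arrest |
| Resuscitated arrest, survived | 1 | 1 | 1 | arrest |
| Non-fatal MI | 1 | 1 | 1 | MI |
| Non-fatal stroke | 1 | 1 | 1 | stroke |
| Fatal stroke | 1 | 1 | 1 | stroke, not death |
| Other fatal vascular event | 1 | 1 | **0** | none |
| Term 'Death', cause in truth non-CV | 0 | 0 | **1** | death |

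**Component rows**
- *Death.* Against CV death, the row loses fatal strokes and other vascular deaths, and gains non-CV deaths coded only as 'Death'.
- *Arrest.* The row gains fatal arrests, which are already in the death row. The MI block carries a non-fatal restriction; the arrest block does not.
- *Stroke.* The row agrees with SAP 6.4.6.3. It gains fatal strokes against the protocol and against SAP 2.2 and 3.8.7.

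**Composite.** Six of the eight types give the same answer under all three definitions. The other two differ in opposite directions: other vascular deaths are missed and non-CV 'Death' cases are added.

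**Illustration only, with assumed rates that have no source in the documents.** Suppose 5-10% of 1,500 subjects have a MACE, 10-20% of those events are fatal, and 10-20% of the fatal events code outside the Cardiac disorders SOC and the stroke HLT.
- MACE: 1,500 x 0.05 = 75 to 1,500 x 0.10 = 150.
- Fatal: 75 x 0.10 = 7.5 to 150 x 0.20 = 30.
- Missed: 7.5 x 0.10 = 0.75 to 30 x 0.20 = 6, that is, about 1 to 6.
- Share of the composite: 0.75/75 = 1% to 6/150 = 4%, before any offset from added 'Death' cases.

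**The case against.** The strongest reply is that little depends on this endpoint. It is exploratory, reported as counts and percentages, and outside the tested hierarchy. The same prespecified terms apply to both arms of a blinded trial. A fatal treatment-emergent vascular event missed by the MACE search would still appear in the fatal TEAE table by SOC and preferred term, and SAEs and deaths are listed (SAP 6.4.8.1). All of that stands. It limits the consequence but does not make the rows match their labels.

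Four stronger readings are tempting, and the documents do not support them:
- *The composite will be wrong.* A reader might infer this from the double entry of fatal arrests and the placing of fatal strokes. The composite counts subjects, so a subject in two rows counts once, and both events already belong as CV deaths. Keeping fatal strokes in the stroke block in fact recovers deaths that the cardiac-death terms would lose.
- *Appendix 5 adds fatal strokes to the SAP's MACE.* It does not; SAP 6.4.6.3 puts no fatality limit on stroke. The conflict is between that section and the protocol, SAP 2.2 and SAP 3.8.7.
- *Every search term is an undeclared change.* The protocol gives no search terms and defers detail to the SAP (Protocol Section 10). Only the stroke wording clearly belonged in SAP Section 8.
- *These are the only clinical outcomes collected.* All AEs and SAEs are collected, and new-onset diabetes and hepatic, renal and neurological events have their own analyses (SAP 6.4.8.1 and 6.4.8.3).

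It can also be argued that treating a death of unknown cause as cardiovascular is a defensible convention. It may be, but the SAP does not state it as one.

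**Conclusion.** The mismatch between definition and derivation holds for two components. CV death is derived as cardiac death plus unspecified death, and resuscitated arrest is derived as any arrest. Separately, the SAP's MACE covers all strokes where the protocol and the SAP's own objectives and collection text say non-fatal, and this is not declared.

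Component counts will depart from their labels if fatal strokes, other vascular deaths, unspecified non-CV deaths or fatal arrests occur. The composite may be off, but only through other vascular deaths missed and non-CV 'Death' cases added, and these pull against each other. The size cannot be computed from the documents; the 1% to 4% illustration rests wholly on assumed rates. The row assignments rest on the coding assumptions stated with the table. No primary or key secondary result is affected. It is a modest point, worth correcting because it is cheap.

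**What to change.** 1. In SAP Appendix 5, item 8, rename the death block to CV death. Define it as fatal SAEs in the Cardiac disorders SOC, the Vascular disorders SOC and the stroke HLT. Check the term list against the dictionary version in use.
2. Show the preferred term 'Death' with unknown cause on its own line, and state whether it enters the composite.
3. Require a non-fatal outcome for the cardiac arrest term, so that a fatal arrest counts once, under CV death.
4. Choose either stroke or non-fatal stroke and use it in Protocol 3.5, SAP 2.2, SAP 3.8.7, SAP 6.4.6.3 and Appendix 5, and bring the protocol synopsis and Protocol 7.1.7 into line. Either way, count fatal strokes in CV death. If all strokes are kept, say that a fatal stroke appears in both rows and once in the composite.
5. List the stroke change in SAP Section 8 if the SAP continues to differ from the protocol.

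The cost is a small edit to the appendix and related wording and a small change to the derivation program. No new data are needed.

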APPENDIX 6. CLINICALLY RELEVANT ADVERSE EVENTS AT THE INJECTION SITE PREFERRED TERMS

Injection site atrophy
Injection site cellulitis
Injection site dermatitis
Injection site eczema
Injection site erythema
Injection site fibrosis
Injection site granuloma
Injection site hypersensitivity
Injection site infection
Injection site inflammation
Injection site ischaemia
Injection site lymphadenopathy
Injection site necrosis
Injection site nerve damage
Injection site photosensitivity reaction
Injection site pruritus
Injection site pustule
Injection site rash
Injection site reaction
Injection site recall reaction
Injection site scar
Injection site thrombosis
Injection site ulcer
Injection site urticaria
Injection site vasculitis
Injection site vesicles
